5.6.2 Secondary Efficacy Analysis

Efficacy endpoints related to RECIST tumor assessment will be analyzed and reported based on the evaluation by IRC and investigators respectively, using the same statistical analysis method. So the analysis methods for DoR, PFS, DCR and percentage change in tumor size are described below regardless of assessment by IRC or investigaors.

5.6.2.1 DoR

The definition and derivation of DoR can be found in Section 4.2.2.1.

DoR will be analyzed and reported by treatment group in a subset of FAS, including patients with an objective response (BOR is confirmed CR or PR).

Number of patients achieving a confirmed objective response and the number (%) of responding patients with event or censored, and the number (%) of responding patients with a duration of response > 3, > 6, > 9 and > 12 months will be presented. Or if data are appropriate, the durable response rate at some milestones (like 3, 6, 9 and 12 months) and the

quartiles (25%, 50%, 75%) of DoR will be provided with 95% CIs based on the Kaplan-Meier method, along with a Kaplan Meier plot.

To demonstrate tumor response episodes over the treatment period, swimmer plot of tumor response overtime will be provided based on patients in FAS. A bar showing the length of treatment duration will be presented for each patient in the plot. Indicators for visit overall responses over time will be added into the bar, so start and end of each response episode can be identified through this plot.

5.6.2.2 PFS

The definition and derivation of PFS can be found in Section 4.2.2.2.

PFS will be analyzed in FAS. The number (%) of patients with event or censored before data cut-off will be reported. Breakdown of events (PD or death) and censors will also be summarized.

The progression-free survival rates (at 3, 6, 9 and 12 months and etc) and quartiles of PFS will be estimated for each treatment group based on Kaplan-Meier method. PFS data will also be displayed graphically using a Kaplan-Meier plot.

5.6.2.3 DCR

Similar to ORR, DCR will be calculated and reported in FAS.

DCR will be reported along with two-sided 97.5% CI based on Exact (Clopper-Pearson) method, by treatment group.

5.6.2.4 Percentage Change in Tumor size

Only tumor size data up to progression and before the start of further anticancer therapy will be included in the analysis.

The absolute values and percentage change from baseline in tumor size will be summarized using descriptive statistics by RECIST visit and treatment group in FAS. The best change from baseline will also be summarized.

Waterfall plots will be displayed by treatment group showing best tumor change from baseline (%) in the vertical axis and each individual patient in the horizontal axis. Positive values indicate tumor growth; on the contrary, negative values indicate tumor reduction. Each patient's percentage change in tumor size will be presented by a separate bar, with the bars ordered from the largest increase to the largest decrease. Reference line at the -30% and 20% change in tumor size levels will be added to the plots, which corresponds to the definition of PR and PD respectively.

To show tumor size change over time, spider plot will also be displayed showing percentage tumor change from baseline (%) for each individual patient in the vertical axis and time from baseline tumor assessment in the horizontal axis.

5.6.2.5 ORR by Investigators

ORR assessed by investigators will be analyzed in FAS using the same analysis method described in Section 5.6.1. But the p value and confidence interval reported will only be considered as descriptive.

5.6.2.6 **OS**

The definition and derivation of OS can be found in Section 4.2.2.6.

Overall survival will be analyzed in FAS. The number (%) of patients with event (death) or censored before data cut-off will be summarized. Breakdown of censors (alive at the end of study, lost to follow-up and etc) may also be summarized.

The overall survival rates (at 3, 6, 9 and 12 months and etc) and quartiles of OS will be estimated for each treatment group based on Kaplan-Meier method. OS data will also be displayed graphically using a Kaplan-Meier plot.

5.6.3 Subgroup Analysis

In addition to the analysis above, confirmed ORR assessed by IRC in part B will be analyzed by subgroup variables below.

- Number of regimens (<3, 3)
- Prior onco-immunotherapy (with, without)
- Prior amivantamab treatment (with, without)
- Brain metastasis at baseline (Yes, No)
- Mutation subtype group (e.g.: A767 V769dup, S768 D770dup and other)
- Race (Asian, White, Other)

Patients with race information missing (not reported) will also be included in the subgroup of 'other'.

- Region (Asia, Non-Asia)
- Age group (<65 years, ≥65 yeas)
- Sex (Female, Male)
- Smoking history (Never, Ever)
- Failure reason for the last line of prior platinum-based chemotherapy (Progression, Toxicity or other)

ORR will be reported along with 95% exact CI based on Clopper Pearson method within each level of the subgroup variables respectively. ORR and it's 95% CI within each level of the subgroup variables will also be presented in forest plot.

If the number of patients is small (less than 10) in a specific level of the subgroup variables, appropriate combination of the levels will be considered for subgroup analysis (in this case subgroup analysis will not be performed for the two-level subgroup variable).

5.6.4 Exploratory Analysis

To show the consistency between the RECIST assessments performed by the IRC and investigators, concordance table will be provided based on the binary variable of objective response (achieving confirmed response or not) derived from IRC or the investigators data.

TTR will be summarized by treatment group in a subset of FAS, including FAS patients who achieved confirmed CR or PR. TTR in days will be summarized as continuous variable in this subset, and the visit of first response will also be summarized as category variable.

The subsequent anti-cancer therapy post the objective disease progression (evaluated by investigators) will also be summarized for better understanding of the patient journey and long-term data.

5.6.5 Multiplicity Adjustment

Considering there are two dose arms in the pivotal study and the primary endpoint will be analyzed within each arm independently, Bonferroni method will be employed to control the family-wise type I error (at one-sided 0.025). That is, the statistical test for primary efficacy endpoint will be performed at one sided significance level of 0.0125, within each dose arm.

5.7 Safety

5.7.1 Adverse Event

Summary tables of AEs by treatment group and overall will be produced in the safety set. Only the TEAEs will be included in the summaries.

An overview table will be created to present the number and percentage of patients with at least one of the following TEAEs, where patients with more than one TEAE in a particular category will be counted only once in that category.

- any TEAE;
- drug-related TEAE;
- TEAE grade 3 or higher;
- drug-related TEAE grade 3 or higher;

- Treatment-emergent SAE;
- drug-related SAE;
- TEAE leading to drug interruption;
- drug-related TEAE leading to drug interruption;
- TEAE leading to dose reduction;
- drug-related TEAE leading to dose reduction;
- TEAE leading to drug discontinuation;
- drug-related TEAE leading to drug discontinuation;
- TEAE with fatal outcome;
- drug-related TEAE with fatal outcome;

The number and percentage of patients reporting each TEAE will be summarized by MedDRA System Organ Class (SOC) and/or Preferred Term (PT). The following summaries will be produced:

- TEAEs, by SOC and PT;
- drug-related TEAEs, by SOC and PT;
- TEAEs of Grade 3 or higher, by SOC and PT;
- drug-related TEAEs of Grade 3 or higher, by SOC and PT;
- TEAEs, by SOC, PT and maximum CTCAE grade;
- drug-related TEAEs, by SOC, PT and maximum CTCAE grade;
- Treatment-emergent SAEs, by SOC and PT;
- drug-related treatment-emergent SAEs, by SOC and PT;
- TEAEs leading to drug interruption, by SOC and PT;
- drug-related TEAEs leading to drug interruption, by SOC and PT;
- TEAEs leading to dose reduction, by SOC and PT;

drug-related TEAEs leading to dose reduction, by SOC and PT;

- TEAEs leading to drug discontinuation, by SOC and PT;
- drug-related TEAEs leading to drug discontinuation, by SOC and PT;
- TEAEs with fatal outcome, by SOC and PT;
- drug-related TEAEs with fatal outcome, by SOC and PT;

Additional tables for common TEAEs may be provided to facilitate the CSR development.

In the above summaries, patients with more than one AE within a particular SOC are counted only once for that SOC. Similarly, patients with more than one AE within a particular PT are counted only once for that PT.

For summaries by maximum severity, patients with multiple AEs within a particular SOC or PT will be counted under the category of their most severe AE within that SOC or PT. If CTCAE grade is missing for a TEAE, it will be counted as missing category in the summary tables by maximum grade.

In all summary tables, the events will be sorted by descending frequency in the overall group, at SOC and/or PT level respectively.

No statistical comparisons of AEs between treatment groups will be performed.

All individual AE data collected will be listed together, and treatment-emergence status will be flagged in the listing. Any adverse events that occur after a patient has received further therapy for cancer will be flagged in the data listings. In addition, listings of serious AEs (SAEs), AEs leading to drug discontinuation, AEs with fatal outcome and all deaths will be produced. If data are appropriate, the number of deaths and primary reason will be summarized by period (from the first dose to 28 days after the last dose; post 28 days after last dose) in the safety analysis set.

5.7.2 Laboratory Data

The laboratory tests as specified in Section 4.3.2 will be summarized by treatment group and overall in the safety set.

For the laboratory test with applicable CTCAE grade criteria, shift tables will be provided to show the shift from baseline CTCAE grade (0 to 4) to the worst grade post-baseline. For the tests (like ALT, AST, ALP, and total bilirubin) where CTCAE grade is not applicable for the baseline value, summary of worst grade post-baseline by baseline status (normal/abnormal) will be provided instead of shift table. In addition, summary tables will be provided to present the maximum grade increase from baseline for each abnormality applicable.

To present the status change in clinical significance from baseline to the worst case (abnormal clinically significant > abnormal not clinically significant > normal) post-baseline, shift tables will be provided for the laboratory tests not covered by CTCAE.

In the shift tables, only the patients with non-missing data at both baseline and the corresponding post-baseline visit(s) will be included.

Number and percentage of patients meeting the criteria in Appendix C during the analysis period (from the first dose date of DZD9008 until 28 days after the last dose) will be reported. Shift table will also be provided to tabulate the AST or ALT elevation status at baseline against the worst case during the analysis period.

Graphic displays may be provided for some laboratory tests of interest (such as tests related to common AEs) to show the trend of change relative to the baseline.

All abnormal laboratory data observed in the study will be included in the individual data listing.

5.7.3 Vital Signs

Vital signs data together with the changes from baseline will be summarized by visit and Final Visit using standard descriptive statistics in the safety set. The body weight and BMI will also be summarized similarly.

All the measurements and change from baseline will be listed in the individual data listing.

5.7.4 Electrocardiograms

The central ECG data will be summarized by treatment group and overall in the safety set, while the local ECG data will be presented in the individual data listing only.

The ECG measurements and changes from baseline will be summarized by visit (and timepoint when applicable) and Final Visit using standard descriptive statistics.

The number and percentage of patients with abnormal ECG measurement meeting each criterion below will be reported respectively, based on the worst (highest) case post-baseline.

- absolute prolongation in QTcF interval (msec):
 - > 450
 - > 480
 - > 500
- Change from baseline in QTcF interval (msec):
 - increases from baseline >30
 - increases from baseline >60

• QTcF > 500 msec and increases from baseline > 60 msec

For the overall ECG interpretation, shifts from baseline to the worst case (abnormal clinically significant > abnormal not clinically significant > normal) post-baseline will be presented in the shift table.

In the shift tables, only the patients with non-missing data at both baseline and the corresponding post-baseline visit will be included.

All the ECG measurements (both central and local) and change from baseline will be listed in the individual data listing, together with the Overall ECG Interpretation.

5.7.5 ECOG

The ECOG performance status will be summarized as category variable by visit and Final Visit in the safety set and also listed in the individual data listing.

5.7.6 Other

The echocardiogram/MUGA, pulmonary function test and ophthalmologic assessment will be listed in the individual data listing.

Parameters below will be summarized with descriptive statistics by visit and treatment group in the safety set.

- Left Ventricular Ejection Fraction (LVEF, %)
- Diffusing capacity of lung for carbon monoxide (DLCO, mL/min/mmHg)
- Forced expiratory volume in one second (FEV1, L)

[figure not shown]
Number and proportion of subjects meeting each criterion below will be reported by treatment group, based on the worst (lowest) LVEF value post-baseline.

- decrease from baseline ≥ 10 $\leq 20\%$ and absolute LVEF $\leq 50\%$
- decrease from baseline \geq 10- \leq 20% and absolute LVEF \geq 50%
- decrease from baseline ≥ 20 $\leq 30\%$ and absolute LVEF $\leq 50\%$
- decrease from baseline \geq 20- \leq 30% and absolute LVEF \geq 50%
- decrease from baseline $\geq 30\%$ and absolute LVEF < 50%
- decrease from baseline $\geq 30\%$ and absolute LVEF $\geq 50\%$

5.8 Pharmacokinetics

The drug concentration and PK Parameters will be analyzed and reported in PKS, as described in subsections below.

Cases listed below will be potentially excluded from statistical analysis and clinical pharmacologist will review and confirm before the final decision for a formal analysis.

5.8.1 Summary of Drug Concentration

Drug concentration data will be analyzed and reported in PKS.

Concentrations of DZD9008 in plasma following single dose and multiple dose (steady state) will be summarized separately by nominal timepoint within each treatment group for subjects with intense PK in PKS. The concentration collected at the overlapped timepoints between intense and sparse PK will be summarized by nominal timepoint and treatment group in PKS. Extra measurements (such as unscheduled or repeat assessments) will not be included in the summary tables, but will be included in individual data listings.

The following summary statistics will be provided for concentration in the summary tables:

- Number of observations
- Number of observations below Lower Limit of Quantification (LLOQ)
- Arithmetic mean calculated using untransformed data
- Standard Deviation (SD) calculated using untransformed data
- The geometric mean (calculated as $\exp[\mu]$, where μ is the mean of the data on a logarithmic scale)
- Geometric coefficient of variation (CV, calculated as $100\sqrt{[\exp(s2)-1]}$, where s is the standard deviation of the data on a log scale)
- Geometric mean \pm SD (calculated as exp[$\mu\pm$ s])

Median

- Minimum
- Maximum

The drug concentration will also be displayed graphically, including the intense PK samples and the trough (pre-dose) concentration from all patients. Plasma concentration will be plotted (on the linear and log-scale) versus time for each individual patient. The geometric mean will also be plotted versus the nominal timepoint, grouped by treatment. And the error bar for geometric mean \pm SD will be added if appropriate.

All drug concentration data collected will be presented in the individual data listing, including the data excluded from analysis and the extra measurements (such as unscheduled or repeat assessments).

Concentration of metabolite (DZ0753) will also be analyzed and reported using the same method.

5.8.1.1 Reporting Concentration below LLOQ

Individual concentrations below the LLOQ of the assay will be reported as NQ (not quantifiable) with the LLOQ defined in the Tables, Listings and Graphs (TLGs). For descriptive statistics:

- 1. If, at a given time point, 50% or less of the plasma concentrations are not quantifiable (NQ), the geometric mean, geometric CV, geometric SD, arithmetic mean, SD and median will be calculated by substituting the LLOQ for values which are NQ.
- 2. If more than 50%, but not all, of the concentrations are NQ, the geometric mean, geometric CV, geometric SD, arithmetic mean and SD will be reported as not calculable (NC). The max value will be reported from the individual data, and the min and median will be set as NQ.
- 3. If all the concentrations are NQ, the median, geometric mean and arithmetic mean will be reported as NQ, and the geometric CV, geometric SD and SD will be reported as NC.

The number of values below LLOQ are reported for each time point along with the total number of collected values. Given that criterion 1 above is met, three observations >LLOQ are required as a minimum for a plasma concentration to be summarised. If only one or two values above LLOQ are available, data are presented as a minimum and maximum with the other summary statistics as NC.

The concentration below LLOQ before the first dose will be reported as zero in the summary table. Although zero is also considered as below LLOQ (reflected in n below LLOQ), the statistics will be calculated based on zero value(s) rather than the rules above.

5.8.2 Summary of Pharmacokinetic Parameters

The derived PK parameters for DZD9008 following single dose and multiple dose (steady state) will be summarized separately by treatment group in PKS.

The parameters required in the summary tables required for each parameter can be found in Table 3 and Table 4. Statistics for each PK parameters will be presented following the Dizal SOP.

Box plots will also be provided for the PK parameters to show the quartiles of the data as well as the outliers.

The PK parameters will be presented in the individual data listing. Data excluded from analysis will also be presented and identified in the listing.

The PK parameters for metabolite (DZ0753) will also be analyzed and reported using the same method.

5.9 Exploratory Endpoints

5.9.1 EQ-5D-5L

The EQ-5D-5L data will be summarized by visit and Final Visit for each treatment group in SS.

The number and percentage of patients with different levels for each item in EQ-5D-5L will be reported. The weighted health state index and VAS score will also be summarized as continuous variable, together with change from baseline.

5.9.2 PRO-CTCAE

PRO-CTCAE data will be summarized with descriptive statistics in SS.

For each selected item from the library, proportion of PRO-CTCAE scores for each item attribute (frequency, severity, interference, amount, presence) will be summarized by visit and Final Visit. Proportions will be calculated based on the number of patients with available data at each visit. Butterfly chart will also be prepared for each item attribute to show the proportion change over time.

In addition, descriptive analysis will be performed for each item attribute to show the percentage of patients with symptom at baseline (PRO-CTCAE score > 0), percentage of patients that show any worsening during the analysis period (change from baseline in PRO-CTCAE score > 0), and percentage of patients that show a worsening to score of 3 or 4 (PRO-CTCAE score ≥ 3 and change from baseline > 0). Proportions will be calculated based on the number of patients with both baseline and post-baseline data available for each item attribute as the denominator.

5.9.3 FACIT GP5

The number and percentage of patients with different responses to FACIT GP5 will be reported by visit and Final Visit for each treatment group in the safety analysis set. Butterfly chart will also be prepared to show the proportion change over time.

In addition, descriptive analysis will be performed to show the percentage of patients bothered by side effect at baseline (FACIT GP5 score > 0), percentage of patients that show any worsening during the analysis period (change from baseline in FACIT GP5 score > 0), and percentage of patients that show a worsening to score of 3 or 4 (FACIT GP5 score ≥ 3 and change from baseline > 0). Proportions will be calculated based on the number of patients with both baseline and post-baseline data available as the denominator.

[figure not shown]
5.9.4 PoM Biomarker

[figure not shown]
If data are available, pEGFR expression level in tumor tissue at baseline and post baseline (cycle 2), as well as percent change from baseline will be summarized by treatment group in the paired biopsy set. Percent change from baseline for each individual will be graphically displayed together with mean (or median) by treatment group.

6. INTERIM ANALYSES

To check futility and also inform the dose selection, one interim analysis will be performed when patients completed at least 2 RECIST assessments in each arm.

If the number of responses is less than or equal to \blacksquare out of \blacksquare patients in the first stage, then the arm will be stopped. A dose arm passing the first stage is considered as a "competitive" arm. When both dose arms become competitive, the response rate of two arms will be compared using stage 1 data to identify the more effective arm. $Pr(P_A \ge P_B| \text{ observation})$, defined as probability of true ORR in arm A higher or equal to arm B given the observation at stage 1 assuming a beta (1,1) prior distribution for both cohorts, is used to determine the

7. DATA HANDLING RULES

7.1 Time points and Visit Windows

Day 1 is defined as the day of first dose of investigational product. Relative days on or after Day 1 are calculated as (assessment date – Day 1 date) + 1. Relative days prior to Day 1 are calculated as (assessment date – Day 1 date). The day prior to Day 1 is Day -1.

The baseline value was defined as the most recent non-missing value before the first dose of investigational product. The data measured on Day 1 will be considered as candidate of baseline, unless there is information indicating that the data are measured after the dosing.

All post-baseline data (except for the PRO data) will be analyzed using nominal study visits as defined in the Study Schedule and CRF, when required. No visit windows will be applied for summary and analysis and only data from scheduled visits will be included in the by-visit summary. For safety data collected by visit, a Final Visit will be defined at which the last valid measurement post-baseline will be reported.

For the summary of safety data based on the worst case post-baseline, both scheduled visits and unscheduled visits within the analysis period (from the first dose to 28 days after the last dose) can be included.

Table 7 Definition of Analysis Visit Window

Data Domain	Analysis Visit	Target Day of Visit (T) ^a	Acceptable Visit Window (Day Range)
PRO-CTCAE/ FACIT	Baseline	1	≤1
171011	Cycle 1 Day 8 Cycle x Day y b	8 $21 \times (x - 1) + y$	2 to 11 T ± 3
	Cycle 7 Day 1	$127 \times (x-1) + y$	T - 3 to $T + 10$ (Day 124 to 137)
EQ-5D-5L	Cycle x Day 1 Baseline	$21 \times (x - 1) + 1$	$T \pm 10$ ≤ 1
	Cycle 3 Day 1 Cycle x Day 1 c	43 $21 \times (x - 1) + 1$	2 to 63 T - 21 to T + 20

Data Domain	Analysis Visit	Target Day of Visit (T) ^a	Acceptable Visit Window (Day Range)
RECIST assessments from IRC	Tumor assessment visit name in CRF	Tumor assessment date collected in CRF	$T \pm 14^{d}$

^a Relative to the date of first dose of DZD9008 (Day 1).

For the PRO data, visit information was not collected for all patients in CRF directly, so the analysis visit windows will be used for the by-visit analyses (Table 7).

RECIST visit from IRC will also be mapped to the corresponding tumor assessment visit collected in CRF, based on the actual tumor assessment date. If there is not date-matched tumor assessment visit in CRF (e.g., additional IRC visits after the patient is evaluated as PD by investigator), the IRC visit will be mapped by increasing the visit number in sequence.

Multiple measurements within the same window will be dealt with as follows:

• If there are multiple measurements within a single analysis visit window, the measurement closest to the target day of the visit window will be used in the analysis. If there is a tie, the later one will be used.

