1.1.2.3 Exploratory objectives

• To collect and store archived tumor samples (if more than one formalin-fixed paraffin-embedded (FFPE) block from a patient, tissue from the most recent one is preferred) or any fresh tumor biopsies (if archived tumor sample is not available) for EGFR Exon20ins confirmation in central laboratory and necessary technical studies

Clinical Study Protocol Drug Substance: DZD9008 Protocol No.: DZ2019E0001

Edition Number: 12.0 Date: July 24,2023

for companion diagnostics development and approval and potential future exploratory research into factors that may influence development of DZD9008.

- To collect and store plasma samples to isolate circulating free tumor DNA (ctDNA) for EGFR Exon20ins mutation testing and necessary technical studies, for liquid biopsy companion diagnostic development and approval.
- To collect and store blood-based samples for future exploratory research on genes/genetic aberrations that may influence response to DZD9008 treatment and/or susceptibility to DZD9008.
- To investigate the effect of DZD9008 on proof-of-mechanism (PoM) biomarkers in tumor biopsy (e.g., EGFR phosphorylation (pEGFR).
- To explore the relationship between DZD9008 exposure and selected endpoints (which may include efficacy, safety, QTc interval etc.), where deemed appropriate.
- To collect and store deoxyribonucleic acid (DNA) for future exploratory research into genes/genetic variation that may influence PK or response to DZD9008, (i.e., absorption, distribution, metabolism, excretion, safety and efficacy).
- To explore the impact of DZD9008 treatment and disease state on health state utility by using EQ-5D-5L health state utility index based on patient reported data.
- To assess AEs of DZD9008 by using subjects reported specific CTCAE symptoms (PRO-CTCAE) and FACIT GP5 questionnaire.

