6.3.5 Other safety assessments

6.3.5.1 Resting 12-lead ECG

Twelve-lead ECGs will be performed at the visit indicated in the Study Plan (see Table 11, Table 12, Table 13, Table 14).

Twelve-lead ECGs will be recorded at the following times:

Part A

Screening

^{*} Beyond what listed in the table, additional urine/serum samples will be collected from all females of childbearing potential at screening (within 7 days of the first dosing), and at treatment discontinuation for a pregnancy test.

Date: July 24,2023

- First dosing day (Cycle 0 Day 1) for dose escalation: pre-dose, 1, 2, 4, 6, 10 and 24 hours post-dosing
- On day 1 and day 9 of food effect cohort in Part A: pre-dose, 1, 2, 4, 6, 10 and 24 hours post-dosing (treatment time might be updated upon emerging human PK data).
- First day of multiple dosing (Cycle 1 Day 1): pre-dose, 1, 2, 4, 6, 10 and 24 hours post-dosing
- Cycle 1 Day 8 and Day 15: pre-dose, 1, 2, 4, 6, 10 and 24 hours post-dosing
- On Day 1 of each subsequent cycles: one assessment at any time during the day
- On occurrence of any cardiac AE
- Discontinuation visit

Part B

- Screening:
 - For sparse PK group: any time on that day for sparse PK group
 - For intense PK group: pre-dose, 2, 4, 6 and 8 hours post dosing (Since there is no dosing at screening, ECG recording should start at a time that would be consistent with planned dosing times at Cycle 1 Day 1 and Cycle 3 Day1 (for baseline purpose).
- Cycle 1 Day 1 and Cycle 3 Day 1: Pre-dose, 2, 4, 6 and 8 hours post-dosing
- Cycle 1 Day 8 and Cycle 1 Day 15: Pre-dose
- Cycle 2 Day 1: Pre-dose
- On Day 1 of each subsequent cycles after Cycle 3: one assessment at any time during the day
- On occurrence of any cardiac AE
- Discontinuation visit

The timing and number of ECGs may be adjusted depending on the emerging PK and safety data.

A 30 minute window will be allowed for ECGs performed at pre-dose and 15 minute window for 1-10 h, and 1 hour window for ECG performed at 24 hours.

Date: July 24,2023

Twelve-lead ECGs will be obtained after the patient has been resting semi-supine for at least 10 minutes prior to times indicated. All ECGs should be recorded with the patient in the same physical position. For each time point three ECG recordings should be taken at about 5 minute intervals. A standardised ECG machine should be used and the patient should be examined using the same machine throughout the study if possible.

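### The SAP gives no baseline role to the time-matched screening ECGs collected in intense-PK patients, so QTcF changes at 2 to 8 hours mix drug effect with time of day

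*SAP*

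**What the plan says.** Protocol 6.3.5.1 sets the Part B screening ECG schedule separately for the two PK groups.

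- Intense-PK group: "For intense PK group: pre-dose, 2, 4, 6 and 8 hours post dosing (Since there is no dosing at screening". The start time is to be "consistent with planned dosing times at Cycle 1 Day 1 and Cycle 3 Day1 (for baseline purpose". The footnote to the ECG row of Table 18 repeats these times.
- Sparse-PK group: "For sparse PK group: any time on that day for sparse PK group".
- On treatment, with no restriction by PK group: "Cycle 1 Day 1 and Cycle 3 Day 1: Pre-dose, 2, 4, 6 and 8 hours post-dosing".

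Each timepoint has three recordings.

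SAP 7.1 gives one general baseline rule: "The baseline value was defined as the most recent non-missing value before the first dose of investigational product". It adds that Day 1 data qualify unless they are known to be post-dose. SAP 4.3.3 averages replicates within a visit and timepoint and does nothing further. SAP 5.7.4 then says: "The ECG measurements and changes from baseline will be summarized by visit (and timepoint when applicable) and Final Visit". It also counts patients whose worst post-baseline QTcF rises by more than 30 or 60 msec, or passes 450, 480 or 500 msec. None of these sections contains an ECG-specific or time-matched baseline.

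**The concern.** The protocol asks some patients for five triplicate ECG timepoints on a day without drug and says that they are for baseline. The SAP then measures every post-dose change from a single pre-dose reading. A change at 6 hours compares an afternoon recording with, typically, a morning one. If QTcF moves over the day without drug, that movement is reported as change from baseline at exactly the hours when the post-dose effect is being looked for.

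Both Part B arms receive DZD9008, so no untreated group shows what the 2 to 8 hour profile would look like without drug. At stake is the reading of a descriptive safety table. ECG is a secondary safety variable in protocol 1.1.2.2, and section 2.3.2 reports hERG inhibition and activity at other cardiac ion channels, so the table will be looked at. The direction of the shift is unknown: it could exaggerate a drug effect or hide one.

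**Working it through.** The plan states no power, sample size or expected value for QTcF, so there is no figure to reproduce. The check compares the two baseline definitions.

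**Which value becomes baseline.** A Cycle 1 Day 1 pre-dose ECG is scheduled for every Part B patient and is later than any screening ECG, so the SAP rule selects it. If it is missing in an intense-PK patient, the rule falls back to the last screening recording, nominally the 8-hour one, which is a different clock time again.

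**What each definition estimates.** Let D(t) be the drug effect at time t, and d(t) the drug-free QTcF at that clock time minus the drug-free QTcF at the pre-dose clock time.

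- SAP baseline: expected change = D(t) + d(t).
- Matched screening baseline: expected change = D(t) + d(t) - d(t) = D(t), provided that the level and daily pattern are similar on the screening and treatment days.

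**Which outputs are touched.**

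| Output | Uses baseline? | Time-of-day shift under the SAP rule |
|---|---|---|
| QTcF >450, >480, >500 msec | No | None |
| Pre-dose changes at C1D8, C1D15, C2D1, C3D1 | Yes | Small: roughly the same clock time |
| Changes at 2, 4, 6, 8 h on C1D1 and C3D1 | Yes | d(t) in full |
| Worst-case >30, >60, and combined >500 and >60 msec | Yes | Present when the worst value is not at the pre-dose clock time |

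**Who can be matched.** Protocol 6.5.1.3 puts 10% to 30% of each arm in the intense-PK group: 0.10 × 103 = 10.3 and 0.30 × 103 = 30.9, so about 10 to 31 patients in a cohort that reaches 103. The SAP cites a memo on dropping a dose, so the other cohort may be smaller. There are 4 × 2 = 8 post-dose timepoints. Sparse-PK patients have the same on-treatment ECGs but only one screening time, so their changes carry the same shift and cannot be matched.

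**Size.** The documents do not give d(t). For an assumed range of -5 to +10 msec, the mean change is off by -5 to +10 msec. To illustrate the effect on a threshold at one timepoint, P(change > 30) = 1 - Φ((30 - D - d)/SD). With assumed D = 0 and SD = 12 msec:

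| Assumed d (msec) | P(change > 30 msec) |
|---|---|
| -5 | 0.2% |
| 0 | 0.6% |
| +3 | 1.2% |
| +5 | 1.9% |
| +10 | 4.8% |

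These are single-timepoint probabilities on assumed inputs. They do not estimate the SAP count, which takes each patient's worst post-baseline value over all visits.

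**The case against.** The strongest reply is that the mismatch has little consequence and that matching has its own price.

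- **Exposure-QTc.** A reader might infer that the exposure-QTc analysis is compromised. Protocol 1.1.2.3 names exposure relationships with endpoints "which may include efficacy, safety, QTc interval etc" as exploratory. However, SAP 2.1.3 lists the exploratory analyses that it covers and this is not among them, so nothing shows that the SAP 7.1 rule would govern it. Such an analysis could still use the screening profile.
- **Only control.** A reader might also infer that the screening day is the trial's sole protection against daily variation. It is not. Doses are taken at about the same time each day, so later pre-dose ECGs are already roughly matched to the Cycle 1 Day 1 pre-dose ECG. Protocol 2.3.5 describes a flat steady-state profile and a half-life near 50 hours, so those comparisons capture much of the steady-state effect.
- **Noise.** Screening can fall up to 28 days before dosing, whereas the Cycle 1 Day 1 baseline is taken the same day. With an assumed true change of 10 msec and no shift, raising the SD from 15 to 18 msec moves P(change > 30) from 9.1% to 13.3% by itself. This is fair for Cycle 1 Day 1. On Cycle 3 Day 1 both baselines are from earlier days: 42 days before for the SAP baseline, and 43 to 70 days (42 + 1 to 42 + 28) for screening.
- **Mixed definitions.** Changing the baseline for 10% to 30% of patients inside shared tables and worst-case counts would make those outputs harder to read.

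All four limit the point. None explains why recordings made for baseline have no baseline role in the SAP.

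**Conclusion.** The point holds as a minor protocol-SAP alignment issue. Under SAP 7.1 and 5.7.4, QTcF changes at 2, 4, 6 and 8 hours on Cycle 1 Day 1 and Cycle 3 Day 1 combine drug effect with any time-of-day shift. The screening profile that could remove the shift in about 10 to 31 patients of a 103-patient cohort is not used for that purpose. That the shift enters the change follows from the definitions; its size and sign cannot be taken from the documents. Its removal rests on the daily pattern being similar on both days.

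A reader might go further and conclude that the reported >30 and >60 msec counts are wrong by a known amount, or that the baseline should be replaced throughout. The documents support neither. No shift or variability is given. Most patients cannot be matched. From Cycle 4 the ECG may be taken at any time of day, so no baseline choice would make the worst-case counts fully clock-matched.

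**What to change.** In SAP 5.7.4, with a matching sentence in SAP 7.1, add for intense-PK patients only, shown separately:

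1. A by-timepoint table of QTcF change on Cycle 1 Day 1 and Cycle 3 Day 1 from the screening ECG mean at the same nominal time.
2. The numbers with increases above 30 and above 60 msec at those timepoints.
3. The number of patients with no matched screening value at each timepoint, without substituting another baseline.

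Keep the existing baseline for the all-patient tables and the worst-case counts, so that no table mixes two definitions. If the sponsor prefers not to add the table, the SAP should say why the screening profile is not used as a baseline.

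The cost is one extra baseline variable and one table; the protocol already schedules the ECGs and sends them to a central vendor up to the primary analysis. The matched changes may be somewhat more variable from day to day because screening can be up to 28 days before dosing, and the table should carry a note to that effect.
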